2. LIST OF ABBREVIATIONS

Abbreviation	Term
ABC	advanced breast cancer
AE	adverse event
AEM	adverse event monitoring
CDK	cyclin-dependent kinase
CI	confidence interval
CRF	case report form
CSA	clinical study agreement
DCF	data clarification form
DCT	data collection tool
ET	endocrine therapy
HER2-	human epidermal growth factor receptor 2-negative
HR+	hormone receptor-positive
IEC	independent ethics committee
IRB	institutional review board
LET	letrozole
LSLV	last subject last visit
MHLW	Minister of Health, Labour and Welfare
NI	non-interventional
NIS	non-interventional study
OS	overall survival
PAL	Palbociclib
PFS	progression-free survival
SAP	statistical analysis plan

3. RESPONSIBLE PARTIES

Principal Investigator(s) of the Protocol

Organization of study operation will be prepared as Appendix 1.

4. ABSTRACT

Not applicable

5. AMENDMENTS AND UPDATES

Amendment number	Date	Protocol section(s) changed	Summary of amendment(s)	Reason
Amendment 1	07 April 2022	Section 9.2.1	description revised	To clarify inclusion criteria
Amendment 1	07 April 2022	Sections 9.6.2, 10.2, and 12	descriptions revised	Based on the findings of Institutional Review Board (IRB)/Independent Ethics Committee (IEC)
Amendment 1	07 April 2022	Sections 9.10.1, 10.6, 10.7, 10.8	Sections added	Based on the findings of IRB/IEC
Amendment 1	07 April 2022	Section 9.7.5	Section added	To conduct interim analysis based on the data at the second data collection
Amendment 1	07 April 2022	Section 6	description revised	To conduct interim analysis based on the data at the second data collection
Amendment 1	07 April 2022		Other minor edits were made	

6. MILESTONES

Milestone	Planned date

PFIZER CONFIDENTIAL

CT24-WI-GL02-RF02 1.0 *Non-Interventional Study Protocol Template For Secondary Data Collection Study*

15-Aug-2018

Page 5 of 26

Start of data collection	15 December 2020
Completion of interim analysis	15 December 2022
End of data collection	31 December 2024
Final study report	30 November 2025

7. RATIONALE AND BACKGROUND

Breast cancer is the most common cancer in women in Japan, with nearly 86,500 new cases diagnosed in 2018 and breast cancer is the fifth leading cause of cancer-related death in Japanese females [1]. Breast cancer prevalence rate of Japanese women by age group began to increase from the 30s, peaked in the latter half of the 40s, after that it remained almost constant, and gradually decreased from the late sixties[2]. Hormone receptor-positive (HR+) breast cancer accounts for approximately 71% of new cases worldwide[3]. Endocrine therapy has been a mainstay of HR+ breast cancer treatment and recommended by the Japanese Breast Cancer Society and international guidelines for initial treatment of HR+ disease[4, 5]. However, hormonal blockade alone provides only modest benefit in women with advanced breast cancer (ABC), with many patients having de novo or acquired resistance to endocrine therapy.

Palbociclib is a selective, oral inhibitor of cyclin-dependent kinases 4 and 6 (CDK4/6) that prevents cell proliferation by blocking cell cycle progression from the G1 to the S phase. In Japan, palbociclib was approved in 2017 for the treatment of HR+/human epidermal growth factor receptor 2-negative (HER2-) inoperable or recurrent breast cancer. The safety and efficacy of palbociclib were investigated in 2 phase 3, randomized, double-blind, placebo-controlled, multicenter trials (PALOMA-2, -3) and have shown significant activity in the first- or subsequent line treatment of HR+/HER2- ABC when combined with endocrine therapy (ET), demonstrated an approximate doubling of progression-free survival (PFS) when compared to ET alone[6, 7]. In Japanese patients with HR+/HER2- ABC, a phase 2, single-arm, open-label study of palbociclib in combination with letrozole as first-line treatment was conducted, and the combination treatment demonstrated effectively 75.0% (90% CI, 61.3%-84.4%) of investigator-assessed 1-year progression-free survival (PFS) probability, with a manageable safety profile[8].

There is limited data regarding the effectiveness of standard subsequent line therapies (chemotherapy, targeted agents or ET) after progression on CDK4/6 inhibitor-based regimens. Recent analyses in the overall population from PALOMA-2 and PALOMA-3 have shown that the type of subsequent therapy was similar between the palbociclib plus ET and placebo plus ET groups and that PFS improvement associated with palbociclib plus ET was retained in subsequent lines of therapy[9, 10]. While overall survival (OS) data are not yet available for Paloma-2, Paloma-3 has demonstrated that in patients sensitive to endocrine therapy, this combination therapy also brings about longer OS than fulvestrant monotherapy

(39.7 months vs 29.7 months; Hazard ratio, 0.92; 95% CI, 0.55–0.94) suggesting that progression on palbociclib has no significant effect on the therapeutic benefit derived from subsequent treatments received [10]. Although these findings in the overall population suggest that the treatment benefit of subsequent therapy was not compromised by palbociclib, in the postmenopausal woman with moderately pre-treated HR+/HER2- ABC, limited benefit from post palbociclib treatment are reported[11].

Real-world data in the United States demonstrated that palbociclib plus letrozole significantly prolonged progression-free survival by 45% versus letrozole alone ($P < .0001$) and significantly improved overall survival by 48% versus letrozole alone ($P < .0001$), according to a retrospective analysis of electronic health records[12].

The data on the effectiveness of palbociclib containing treatment sequence in Japanese patients are very limited. The health insurance system, available treatment option and healthcare outcomes are different in countries[13]. These differences may influence clinical outcomes of palbociclib in each country. To explore the effectiveness of palbociclib as first-line treatment in Japan, this non-interventional study was planned to follow up the OS and also to investigate the type and duration of subsequent therapies after palbociclib treatment in the phase 2 study conducted in Japan.

8. RESEARCH QUESTION AND OBJECTIVES

Primary objective

To evaluate overall survival (OS) in Japanese patients with HR+/HER2- advanced breast cancer who have been treated with palbociclib plus letrozole in first-line setting

Secondary objective

To describe the type and duration of subsequent therapy after palbociclib plus letrozole treatment in Japanese patients with HR+/HER2- advanced breast cancer

9. RESEARCH METHODS

9.1. Study design

This is a retrospective, multicenter, observational study in Japan. The primary objective is to evaluate OS in Japanese patients with HR+/HER2- advanced breast cancer who have been treated with palbociclib plus letrozole. This observational study was planned as follow-up study of Japanese phase 2 study of palbociclib (NCT01684215, phase 2 portion of A5481010 study, hereafter described as J-Ph2).

In J-Ph2, 43 patients were enrolled, and 42 patients were treated with palbociclib plus letrozole. At the study completion of J-Ph2 [Last Subject Last Visit (LSLV): 25 October 2018], 8 deaths were reported. Of the remaining 34 patients without death reported, 4 patients refused further follow-up and 30 patients were under follow-up for survival.

For the 30 patients under follow-up for survival in J-Ph2, OS and subsequent therapy data will be retrospectively collected from individual patient medical records (See Section 9.3 and 9.4 for detail). If the patient had been transferred to another hospital, the investigator will be asked to collect data as much as possible from the hospital. The investigator will complete paper-based case report forms (CRFs) at study initiation at each study site and at an annual reporting period set by the sponsor. Patient demographics and other relevant data collected in J-Ph2 will be used and matched with data collected in this study through patient IDs for analysis.

For 8 patients with OS events confirmed in J-Ph2 and 4 patients who refused further follow-up in J-Ph2, data collected in J-Ph2 will be used for analysis.

9.2. Setting

Thirty patients who participated, treated with palbociclib plus letrozole, and under follow-up for survival in J-Ph2 will be enrolled in this study for data collection. See Appendix 2 for inclusion and exclusion criteria in J-Ph2.

9.2.1. Inclusion criteria

Patients must meet all of the following inclusion criteria to be eligible for inclusion in the study:

1. Participated, treated with palbociclib plus letrozole in J-Ph2, and was under follow-up for survival at the study completion of J-Ph2.
2. For patients who are still alive and have routine visits to the study site, evidence of a personally signed and dated informed consent document indicating that the patient has been informed of all pertinent aspects of the study. For patients who are still alive and had been transferred to another hospital, evidence that the patient has been informed of all pertinent aspects of the study and oral or written informed consent is obtained. For patients who had already passed away, the conduct of this study will be disclosed, and the patients' legally acceptable representatives will be guaranteed an opportunity to refuse data collection for the patients in accordance with the Ethical Guidelines for Medical and Health Research Involving Human Subjects.

9.2.2. Exclusion criteria

There are no exclusion criteria for this study.

9.3. Variables

The same patient IDs will be used for this study and J-Ph2. Data collected in this study will be combined and evaluated with J-Ph2 data, including patient demographics, study treatment, and baseline tumor assessment, through matching with patient IDs. Variables and data sources are described in Table 1. Detailed definitions will be included in the statistical analysis plan (SAP).

Table 1. Variables in this study

Variable	Role	Data source(s)
Overall Survival	Outcome	J-Ph2 database A5481154 database
Type of subsequent therapy	Outcome	J-Ph2 database A5481154 database
Duration of subsequent therapy	Outcome	J-Ph2 database A5481154 database
Clinical response of subsequent therapy	Outcome	A5481154 database
Palbociclib dose modification	Exposure, Outcome	J-Ph2 database A5481154 database
Palbociclib treatment duration	Exposure, Outcome	J-Ph2 database A5481154 database
Letrozole treatment duration	Exposure, Outcome	J-Ph2 database A5481154 database
Demographic and baseline characteristics	Baseline characteristics	J-Ph2 database

9.4. Data sources

9.4.1. Data to be collected in this study

Data to be collected in this study is described in Table 2. See Section 9.4.2 and 9.4.3 for data collection time point and data collection methods.

Table 2. Data to be collected in this study

CRF	Variables
Informed consent	Patient status at study initiation ⁴
	Informed consent obtained
	Date of informed consent
Survival status	Survival status
	Date last known to be alive
	Date of death
	Cause of death
Subsequent therapy	Drug name of subsequent therapy
	Start and Stop date of subsequent therapy
	Clinical response of subsequent therapy ¹
PAL+LET exposure	Total daily dose ²
	Start and Stop date of each dose ³
	Reason for dose change ²
PAL+LET discontinuation	Date of treatment discontinuation ³
	Reason for treatment discontinuation ³
	Disease site and tumor assessment at treatment discontinuation

Abbreviation; LET=letrozole, PAL=palbociclib

1. Clinical response of subsequent therapy will be evaluated with Complete response, Partial response, Stable disease, Progression disease, and Unknown. See Section 9.4.1.1. for detail.
2. Palbociclib only
3. Data will be collected for palbociclib and letrozole, respectively
4. Patient status at study initiation will be collected as alive and has routine site visit, alive and had transferred to another hospital, dead

9.4.1.1. Assessment

Clinical response of subsequent therapy

Clinical response of subsequent therapy will be evaluated with Complete response, Partial response, Stable disease, Progression disease, and Unknown. These are not any protocol-specified criteria and/or method for response evaluation, and this will be recorded based on investigator's discretion (eg, radiology reports, patients' medical chart).

- Complete response will be selected where "Complete response" has been recorded at any time on treatment.
- Partial response will be selected where "Partial response" has been recorded at any time on treatment without Complete response recorded.
- Stable disease will be selected (1) if the treatment continued for a minimum of 24 weeks or (2) if the treatment discontinued within 24 weeks but the initial response was not Progressive disease, without Complete or Partial response recorded at any time on treatment.

- Progressive disease will be selected if the treatment discontinued within 24 weeks and the initial response was Progressive disease without subsequent Complete or Partial response recorded.

9.4.2. Data collection time point and Data collection period

In this study, data will be collected with paper-based CRFs. The Investigator will complete CRFs for all the patients who remain in follow-up and submit them to the sponsor at the below time points;

1. Study initiation at each study site
2. Annual reporting period set by the sponsor (eg, every April)

For each patient, data collection will be continued until death unless patients withdraw consent or if the study gets sufficient OS events.

For the study, data collection will be continued until sufficient number of OS events are obtained to determine median OS.

9.4.3. Data collection method

Relevant CRFs will be completed according to the patient status at each data collection time point.

At the study initiation at each study site

Investigators will complete the CRF for “Informed consent” and relevant CRFs according to patient status at last visit of J-Ph2 and current patient status (see Table 3 in detail). For example, if patient was receiving palbociclib plus letrozole treatment at last visit of J-Ph2 and the patient still receives palbociclib plus letrozole, investigator will complete CRFs for “Informed consent”, “Survival status” and “PAL+LET exposure”. See Appendix 3 for each patient status at last visit of J-Ph2.

Table 3. CRFs to be completed at study initiation at each study site

Patient status			CRF to be completed
Case	At last visit of J-Ph2	At study initiation at study site	
1	PAL+LET treatment ongoing	PAL+LET treatment ongoing	- Informed consent - Survival status - PAL+LET exposure
2		PAL+LET treatment discontinued and OS follow-up	- Informed consent - Survival status - Subsequent therapy - PAL+LET exposure - PAL+LET discontinuation
3		Death	Same with Case 2
4	PAL+LET treatment discontinued and OS follow-up	OS follow-up	- Informed consent - Survival status - Subsequent therapy
5		Death	Same with Case 4

Abbreviation; LET=letrozole, OS=overall survival, PAL=palbociclib

At the annual reporting period

Investigators will complete the relevant CRF according to patient status at previous and current reporting period (see Table 4 in detail). For example, if the patient status was “PAL+LET treatment discontinued and OS follow-up” at previous reporting period and current patient status is “Death”, investigator will complete CRFs for “Survival status” and “Subsequent therapy”).

Table 4. CRFs to be completed at annual reporting period

Patient status			CRF to be completed
Case	At previous reporting period	At current reporting period	
1	PAL+LET treatment ongoing	PAL+LET treatment ongoing	- Survival status - PAL+LET exposure
2		PAL+LET treatment discontinued and OS follow-up	- Survival status - Subsequent therapy - PAL+LET exposure - PAL+LET discontinuation
3		Death	Same with Case 2
4	PAL+LET treatment discontinued and OS follow-up	OS follow-up	- Survival status - Subsequent therapy
5		Death	Same with Case 4

Abbreviation; LET=letrozole, OS=overall survival, PAL=palbociclib

9.5. Study size

The number of patients eligible for this study is 42 who participated and were treated with palbociclib plus letrozole in J-Ph2.

9.6. Data management

Investigators will fill out relevant CRFs based on source documents (eg, patients' medical chart) with a pen, ballpoint pen, etc. After the completion of CRFs, the investigator will promptly submit them to the sponsor by mail.

When receiving a query from the sponsor on the completed CRF (ie, Data Clarification Form [DCF]), investigators will reconfirm the information on source documents, fill out the DCF as required, and submit the DCF to the sponsor.

9.6.1. Case report forms (CRFs)/Data collection tools (DCTs)/Electronic data record

As used in this protocol, the term CRF should be understood to refer to either a paper form or an electronic data record or both, depending on the data collection method used in this study.

A CRF is required and should be completed for each included patient. The completed original CRFs are the sole property of Pfizer and should not be made available in any form to third parties, except for authorized representatives of Pfizer or appropriate regulatory authorities, without written permission from Pfizer. The investigator shall ensure that the CRFs are securely stored at the study site in paper form and will be secured in a locked room to prevent access by unauthorized third parties.

The investigator has ultimate responsibility for the collection and reporting of all clinical, safety, and laboratory data entered on the CRFs and any other data collection forms (source documents) and ensuring that they are accurate, authentic/original, attributable, complete, consistent, legible, timely (contemporaneous), enduring, and available when required. The CRFs must be signed by the investigator or by an authorized staff member to attest that the data contained on the CRFs are true. Any corrections to entries made in the CRFs or source documents must be dated, initialed, and explained (if necessary) and should not obscure the original entry.

The source documents are the hospital or the physician's chart. In these cases, data collected on the CRFs must match those charts.

9.6.2. Record retention

To enable evaluations and/or inspections/audits from regulatory authorities or Pfizer, the investigator agrees to keep records, including the identity of all participating patients (sufficient information to link records, e.g., CRFs and hospital records), all original signed informed consent documents, copies of all CRFs, safety reporting forms, source documents, detailed records of treatment disposition, and adequate documentation of relevant correspondence (e.g., letters, meeting minutes, and telephone call reports). The records

should be retained by the investigator according to local regulations or as specified in the clinical study agreement (CSA), whichever is longer. The investigator must ensure that the records continue to be stored securely for so long as they are retained.

If the investigator becomes unable for any reason to continue to retain study records for the required period (e.g., retirement, relocation), Pfizer should be prospectively notified. The study records must be transferred to a designee acceptable to Pfizer, such as another investigator, another institution, or to an independent third party arranged by Pfizer.

Study records must be kept for a minimum of 15 years after completion or discontinuation of the study, unless if required by applicable local regulations.

The investigator must obtain Pfizer's written permission before disposing of any records, even if retention requirements have been met. Study records will be disposed appropriately according to each site regulation.

9.7. Data analysis

Detailed methodology for summary and statistical analyses of data collected in this study will be documented in a statistical analysis plan (SAP), which will be dated, filed and maintained by the sponsor. The SAP may modify the plans outlined in the protocol; any major modifications of primary endpoint definitions or their analyses would be reflected in a protocol amendment.

For the purposes of this study, analyses will be descriptive in nature. All variables will be summarized descriptively through the tabular and graphical display of means, standard deviations, medians, ranges of continuous variables of interest, and proportions and frequency distributions for categorical variables. No formal hypothesis testing is planned.

Data collected in this study will be combined and evaluated with J-Ph2 data, including patient demographics, study treatment, and baseline tumor assessment, through matching with patient IDs.

9.7.1. Definition of analysis set

Analysis set is defined as all patients who enrolled and have been treated in the J-Ph2 study excluding alive patients without written or oral informed consent obtained.

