3 STUDY DESIGN

This is a Japanese, multicenter, retrospective, observation study. This observation study is designed as a follow-up study to the Japanese phase 2 study of palbociclib (NCT01684215, the phase 2 part of Study A5481010; hereinafter, J-Ph2). In J-Ph2, 43 subjects were enrolled and 42 received palbociclib plus letrozole. Eight deaths were reported at the end of J-Ph2 (i.e., last subject last visit [LSLV], October 25, 2018). Of the remaining 34 subjects with no reported deaths, 4 refused further follow-up and 30 were being followed up for survival.

Medical charts of those 30 subjects in the post-J-Ph2 survival period will be used to retrospectively collect OS and subsequent-treatment data. For subjects transferred to another hospital, the investigator will be requested to make his/her utmost efforts to collect data from the hospitals to which the subjects were transferred. The investigator will complete paper-based case report forms (CRFs) at the start of the study at each site and during the annual reporting period specified by the sponsor. Subject IDs assigned in J-Ph2 will be used to collate the subject demographics and other relevant data between this observation study and J-Ph2 and to analyze the data.

Eight subjects with OS events confirmed in J-Ph2 and 4 who refused to continue follow-up after J-Ph2 will be analyzed based on data collected in J-Ph2.

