5 ANALYSIS SET

The analysis set is a population of subjects who were enrolled in J-Ph2 and received the investigational product, excluding surviving subjects who did not give written or oral consent.

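### The OS analysis-set rule, read literally, drops the 4 phase 2 refusers whom the design sections keep, and it removes non-consenting patients only if they are alive

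*Protocol*

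**What the plan says.** Protocol 9.7.1 defines one analysis set: everyone enrolled and treated in J-Ph2, "excluding alive patients without written or oral informed consent obtained". SAP 5 has the same rule, "excluding surviving subjects who did not give written or oral consent". Neither makes an exception.

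The design sections treat one group separately. Protocol 9.1 says that for "4 patients who refused further follow-up in J-Ph2, data collected in J-Ph2 will be used for analysis"; SAP 3 agrees: "4 who refused to continue follow-up after J-Ph2 will be analyzed based on data collected in J-Ph2". Protocol 9.5 states: "The number of patients eligible for this study is 42".

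Consent is sought from a narrower group. Protocol 9.2 says that thirty patients "under follow-up for survival in J-Ph2 will be enrolled in this study for data collection", and inclusion criterion 1 in 9.2.1 requires that the patient "was under follow-up for survival at the study completion of J-Ph2". Living patients give written or oral consent. For patients already dead, 9.2.1 and 10.2 give the legal representative an opportunity to refuse data collection.

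On timing, note 4 to Table 2 reads "Patient status at study initiation will be collected as alive and has routine site visit", with transferred and dead as the other categories. This field is on the Informed consent form, which is completed at site initiation (Table 3) and is not among the annual forms (Table 4).

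Protocol 9.7.2 censors a patient without confirmed death at the last date known alive. SAP 7.1.2 plans no sensitivity analysis of OS. SAP 7.6 will summarise consent and survival status.

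**The concern.** There are two separate problems.

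First, the operative definition conflicts with the design. The 4 refusers have no reported death and never enter this study's consent process. A programmer who applies 9.7.1 or SAP 5 as written would remove them, against 9.1, SAP 3 and the 42 in 9.5. The primary result is a single Kaplan-Meier median with its 95% CI. Data collection runs until there are enough OS events to determine that median (9.4.2, SAP 3.1), so the set has to be settled before events are counted.

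Second, membership depends on the outcome. If a patient among the 30 is alive and does not consent, she leaves the set together with the event-free J-Ph2 time already held. A similar patient who died before being asked stays in. Selective loss of survivors pulls the curve down, and no planned analysis would show whether this happened.

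**Working it through.** **Counts (Protocol 9.1, SAP 3).** 43 enrolled, 42 treated, 8 deaths by last subject last visit (LSLV). 42 - 8 = 34; 34 - 4 refusers = 30. Check: 8 + 4 + 30 = 42, which reproduces 9.5. Under the literal rule, 42 - 4 = 38 before any further non-consent. The crude share dead at LSLV is 8/42 = 19.0% or 8/38 = 21.1%.

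**Where the curve reaches 0.5.** Assume that the 8 deaths come first, then the refusers' censoring, then the 30 with no other censoring.
- n = 42: S = 34/42 = 0.810 after 8 deaths. After 11 more, 34/42 x 19/30 = 0.513; after 12 more, 34/42 x 18/30 = 0.486. The median falls at death 20.
- n = 38: S = 30/38 = 0.789 after 8 deaths. After 11 more, 30/38 x 19/30 = 0.500 exactly. The median falls at death 19.
- Refusers kept, 2 living non-consenters removed: 32/40 x 17/28 = 0.486, death 19. Removing 4 or 5 gives death 18.

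**Size in months: illustration only.** The documents give no refusal rates, survival curve or first-dose dates. Assumed: Weibull OS, curve A (shape 2, median 84 months) or B (shape 1.5, median 100 months); 42 to 54 months of follow-up at LSLV; exactly 8 deaths by LSLV; 4 refusers censored at LSLV. Site initiation is taken as 15 December 2020, 25.7 months after LSLV, and end of data as 31 December 2024, 74.2 months after. Where a representative refuses, the patient is censored at LSLV. There were 10,000 runs per curve, and the figure is the median over runs of the Kaplan-Meier median.

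| Scenario | A | B |
|---|---|---|
| Full participation, refusers kept | 85.2 | 102.2 |
| Only the 4 refusers dropped | 82.1 | 97.2 |
| Same, midpoint taken when S = 0.5 | 83.7 | 99.7 |
| Living non-consent 10%, no representative refuses | 82.5 | 98.8 |
| Living 20%, representatives 0% | 79.6 | 95.4 |
| Living 10%, representatives 10% | 84.4 | 101.0 |
| Living 20%, representatives 20% | 83.5 | 99.3 |
| Living 10%, representatives 30% | 87.7 | 104.8 |

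The sampling SD of the Kaplan-Meier median is 8.6 months (A) and 11.5 (B, over the 93% of runs that reach a median). Every shift is below one SD.

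**Keeping living non-consenters, censored at LSLV.** When only the living decline, this gives 83.4 / 100.4 at 10% and 81.2 / 98.0 at 20%. The shares recovered are 0.9/2.7 = 33% and 1.6/5.6 = 29% (A), and 1.6/3.4 = 47% and 2.6/6.8 = 38% (B): less than half each time. At 10% living and 30% representatives it gives 88.5 / 106.0, slightly further from full participation than the present rule.

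**The case against.** The best defence is that a specific statement governs a general one. Protocol 9.1 and SAP 3 say outright that the 4 are analysed, and the consent in 9.7.1 is most naturally the consent sought from the 30. The refusers' vital status after refusal is also unknown, so 'alive' does not fit them well. This stands as to intent. A reader might infer that the sponsor plans to analyse 38 patients, but the documents do not support that. What remains is that the definition in both documents says something else.

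A reader might also infer that the date for judging 'alive' is open, or that no rule covers a representative's refusal. Neither holds. The Informed consent form fixes status at site initiation, although 9.7.1 does not say so. A dead patient whose representative refuses stays in the set, because only living patients are excluded, and 9.7.2 censors her at the last date known alive.

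The strongest inference would be that the plan biases OS downward. That holds only for living non-consent taken alone. Representatives' refusals act upward, and the balance is unknown. The study is also descriptive, and 9.9 already names incomplete data and small size as limitations. These points limit the weight of the finding, but they do not make the rule correct as written.

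**Conclusion.** The conflict over the 4 refusers is established with high confidence: 38 at most under the literal definition, 42 under 9.1, SAP 3 and 9.5. One death separates the two medians under the ordering assumption. The -3.1 (A) and -5.0 (B) months for dropping the refusers describe a literal reading that the design sections reject, and about half of that comes from how software treats S = 0.5 exactly.

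The dependence of membership on outcome is real as a rule, but its effect cannot be sized from the documents. It is zero if every living patient consents and no representative refuses. The assumed scenarios run from -6.8 to +2.6 months, all within sampling error. This is a minor to should-fix correction to a primary-analysis definition and does not undermine the study.

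**What to change.** 1. In Protocol 9.7.1 and SAP 5, state that the 4 refusers are included with J-Ph2 data, censored at the last date known alive. State that the exclusion refers to this study's consent among the 30, with 'alive' judged at site initiation, as Table 2 already records. This needs wording only and no new data.
2. In SAP 7.1.2, replace the not-applicable entry with a sensitivity Kaplan-Meier analysis of all 42 treated patients cut at J-Ph2 LSLV. With 8 deaths in 42 it gives landmark OS and cannot show the effect on the median. It is one extra run on data already held, but use of decliners' data depends on the IRB and on J-Ph2 consent terms that are not in the documents. Beside the primary result, report the numbers of living non-consenters and of representatives' refusals.
3. Reword 9.5 to give 30 patients eligible for new data collection and 42 treated patients in the source population.

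Optional, only if the IRB and the J-Ph2 consent allow: keep living non-consenters with their J-Ph2 data. This removes only part of the bias and can be slightly worse if representatives refuse much more often than living patients.
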